#### 9.7.3.2.2 *Effect estimation – Congenital malformations*

A crude and a PS-weighted (section 9.7.3.2.3) logistic regression model will be used to estimate the Odds Ratios (OR) of CM with 95% CI in offspring paternally exposed to valproate monotherapy within 3 months prior to LMP2 date compared to the reference group comprised of offspring paternally exposed to lamotrigine or levetiracetam (composite monotherapy) in the same time period. Inclusion of covariates not retained in the PS (section 9.7.3.2.2) will be considered in the logistic model in the event of imbalance in prognostically important variables.

Multiple offspring per father is possible and will introduce within-family dependencies into the data. Therefore in the analyses, paternal clustering will be taken into account by correcting standard errors with sandwich estimators (38).

For purposes of the secondary objective analysis, a first logistic model will be performed irrespective of clusters classification (section 9.3.1.3). A second logistic model will be performed including the exposure intensity variable (estimated based clusters as by application of kmeans methodology) (section 9.3.1.3), as an effect modifier, i.e. the interaction exposure\*k-means will be included in the model. Advantages and disadvantages of these approaches are reported in section 9.7.3.2.1.

#### 9.7.3.2.3 *Propensity-score*

Separate PS models will be constructed for the primary and secondary analyses. The PS will reflect the probability of an offspring being assigned to valproate or the comparator exposure group (lamotrigine/levetiracetam), given a set of observed covariates (these being different for the primary and secondary analyses). These PS will then be used to equate the groups of offspring paternally exposed to valproate with offspring paternally exposed to lamotrigine/levetiracetam based on observed covariates.

The process is as follows: All potential confounders (section 9.3.3), as reported in literature, will be considered for inclusion in each PS model (39). Also, variables that are unrelated to the exposure but related to the outcome (section 9.3.3) will be included in the PS model. The inclusion of these variables will increase the precision of the estimated exposure effect without increasing bias. In contrast, including variables that are related to the exposure but not the outcome can decrease the precision of the estimated exposure effect without decreasing bias (39). Candidate covariates will be considered to enter the model if the OR or relative risk in a single association with the outcome is higher than 1.1 or lower than 0.9. In order to model the PS for the analysis of each of the two outcomes, three model approaches will be used and compared. The first approach will consist of a logistic regression model with all potential confounders associated with the outcome. Continuous covariates will be modelled using restricted cubic splines as they not only allow for non-linearity, but are also associated with superior model fit at the tails of distributions (40). An attempt to prevent overfitting will be made by specifying 4 knots at 5, 35, 65 and 95% based on Harrell's recommended percentiles (41). Additionally, two-way interactions will be included only for variables which have been identified by a clinician as clinically meaningful. The second modelling approach will be the use of a random decision forest model (42). The advantage of this approach is that interactions between covariates are by definition incorporated into the model and strong predictors and interactions can thus be identified. The random forest model extends easily to multiple outcomes. Finally, the third modelling approach will be a logistic regression informed by the random forest model. In this approach, data-driven identification of interactions as identified by the random forest model will be incorporated into the logistic regression model.

Once the propensity scores are estimated (separately for the primary and secondary outcome cohorts) they will then be used as weights in the inverse probability of treatment weights approach to balance differences in covariate distribution between offspring paternally exposed to valproate and offspring paternally exposed to lamotrigine/levetiracetam in the adjusted analyses. PS weighting will be used instead of matching for increased generalisability and to avoid the exclusion of patients from the adjusted analyses due to lack of matches (43–46); this is deemed as particularly important in situations where the outcome of interest is relatively rare or infrequent.

For each PS model, the distributions of estimated propensity scores will be visually compared across the three models, separately for the primary and secondary outcome. Selection of the best models for the primary and secondary outcome cohorts will be based on the balance achieved in the weighted exposure groups after using inverse probability of treatment weights. Only the best PS models for the primary and secondary outcome cohorts will then be used to apply inverse probability of treatment weights in the multivariate analysis.

The best PS modelling approach might not be the same for the two cohorts, and similarly the covariates included in the PS model will differ as the two outcomes have different risk factors and confounders.

A sensitivity analysis to compare the results from the PS-weighted approach with the traditional approach of covariate adjustment will be performed, as reported in section 9.7.5, for both primary and secondary composite outcomes, using the composite lamotrigine/levetiracetam monotherapy comparator.

#### **9.7.4 Exploratory objective analyses**

For the *exploratory analyses*, offspring maternally exposed to AEDs (including valproate, lamotrigine and levetiracetam) *in utero*, or during 3 months prior conception, as well as offspring from a mother with a history of epilepsy, will be excluded. For the *exploratory analyses related to the primary outcome*, offspring exposed to AEDs and/or diagnosed with epilepsy after birth will be excluded.

For exploratory objective 5, for offspring paternally exposed to AED polytherapy, summary cohort characteristics and univariate analysis (section 9.7.3.1) will be performed to describe the putative risk factors and frequency of the primary composite outcome (NDD, including ASD) and for the secondary composite outcome (CM) for offspring paternally exposed to valproate (in combination with other AEDs excluding lamotrigine and levetiracetam) and offspring paternally exposed to levetiracetam/lamotrigine in polytherapy (i.e. polytherapy including at least one of them, and excluding valproate) at the time of conception.

For exploratory objective 6, to explore potential for unmeasured family-related confounding factors (such as genetic liability for neuropsychiatric conditions or congenital malformations and early postnatal environmental influences), an exploratory sibling-matched descriptive analyses will be conducted, separately, on the primary composite outcome (NDD, including ASD) and the secondary composite outcome (CM) whereby only families with paternal valproate exposure-discordant siblings will be included (at least one offspring with paternal valproate exposure and one offspring without exposure). For this analysis, summary cohort characteristics and univariate analysis (section 9.7.3.1) will be performed to describe the subgroups and identify potential risk factors for the composite primary and secondary outcomes of interest, respectively.

For exploratory objective 7, which is to investigate the risk of CM in live offspring paternally exposed to valproate (monotherapy), compared to lamotrigine or levetiracetam (composite monotherapy) treatment at the time of conception in Sweden, the descriptive (section 9.7.2), and comparative (section 9.7.3.2) analyses will be presented separately. This is because the population for analysis is comprised of live births only and therefore is systematically different to the cohorts for CM analysis in Norway and Denmark

For exploratory objective 8, on the basis of lack of knowledge of the likely pattern of CM in offspring paternally exposed to valproate, it is of interest to describe the spectrum CMs according to the body system organ class affected from the malformation (see classification in section 9.3.2.2). Therefore, an exploratory objective is proposed to describe the spectrum of sub-types by organ class, with stratification as major or minor CM where feasible.

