### Exploratory objectives

[figure not shown]
5. To describe the putative risk factors and frequency of NDD, including ASD, as well as CM in offspring paternally exposed to valproate (in combination with other AEDs) and to other AEDs (in combination with other AEDs, excluding valproate) at the time of conception.
6. To describe the risk factors and frequency of NDD, including ASD, as well as CM in paternally and maternally matched exposure-discordant (valproate vs lamotrigine/levetiracetam monotherapy) siblings at conception.
7. Investigate the risk of CM in live offspring paternally exposed to valproate (monotherapy), compared to lamotrigine or levetiracetam (composite monotherapy) treatment at the time of conception in Sweden.
8. To describe the frequency of CM by target body system organ class in live and non-live offspring paternally exposed to valproate (monotherapy), and to lamotrigine or levetiracetam (composite monotherapy) treatment at the time of conception.

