#### Inclusion criteria for data extraction

- Singleton pregnancies, with known pregnancy-length of at least 12 weeks within the study time period;
- Pregnancies linked to both mother and father within the study time period;
- Father with a continuous enrolment in the database for  $\geq 12$  months prior to linked mother LMP2 date;
- Father with at least one AED in the data available.

For Sweden the inclusion criteria are slightly different, as only live births can be included:

- Singleton pregnancies resulting in live births
- Pregnancies linked to both mother and father within the study time period;
- Father with a continuous enrolment in the database for  $\geq 12$ -months prior to linked mother LMP2 date;
- Father with at least one exposure to AED during 192 days prior to 28 days after LMP2 date

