### 9.3.1 Exposure definition and measures

Within the AEDs, the primary exposure of interest is the dispensation of valproate. Brand names and generics of all forms of valproate salts will be considered (sodium valproate, valproic acid, valproate semisodium and valpromide) and summarized under the term “valproate”. Valproate will be identified using Anatomical Therapeutic Chemical (ATC) code N03AG01.

*Drug exposure of the offspring is based on the use of AEDs by the father during a risk window prior to conception. Since the spermatogenic cycle is approximately 2.5 months, the risk window considered here is three months prior to conception. Further details are presented in section 9.3.1.3*

As reported in section 9.7.3.2, in the primary analysis, paternal exposure to valproate (monotherapy) will be compared to paternal exposure to lamotrigine or levetiracetam (composite monotherapy). These drugs are generally associated with lower risk of teratogenicity for the offspring of women, however it is unknown whether the effect is the same in men. Lamotrigine and levetiracetam will be identified using ATC codes N03AX09 and N03AX14, respectively. Since polytherapy is indicated for medically refractory epilepsy (14), in order to avoid the risk of disease severity bias associated to polytherapy, evaluation of AED exposure according to monotherapy is preferred for comparative analyses. In this section, definitions of monotherapy and polytherapy are only discussed for AEDs. Co-medications (other than AEDs) are defined in section 9.3.3 (Potential confounding variables). Monotherapy is defined as the exposure to a single AED, whilst polytherapy is defined as any combination of AEDs (including valproate among the exposed and excluding valproate among the unexposed), simultaneously or in sequence, within the 3-months risk window. For example, switching to or switching from an AED other than valproate, lamotrigine or levetiracetam, will be considered as polytherapy, and the offspring of these fathers will be excluded from the comparative analyses. This is because a washout period is not possible in clinical practice since subjects may not be unexposed for seizure control. Including people who were exposed to more drugs of the same class, in the period of interest, could lead to uncertainty in defining which drug is associated with the outcome.

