Dyslexia and other symbolic dysfunctions, not elsewhere classified	R48
Hyperkinetic disorders	F90
Specific developmental disorder of motor function	F82

This sensitivity analysis for the narrow NDD composite case definition only will be conducted in three parts:

- a. Replication of the primary objective, with descriptive and comparative analyses as applied to the primary outcome cohort. Meta-analysis may be applied.
- b. Replication of exploratory objective 5, with summary cohort characteristics and univariate analysis (section 9.7.3.1) performed to describe the subgroups and the risk factors for the narrow NDD composite outcome for offspring paternally exposed to valproate in combination with other AEDs (AED polytherapy) and offspring paternally unexposed to valproate but exposed to other AEDs (any combination) at the time of conception.
- c. Replication of exploratory objective 6, with an exploratory sibling-matched descriptive analyses conducted on the narrow NDD composite outcome whereby only families with paternal valproate exposure-discordant siblings will be included (at least one offspring with paternal valproate exposure and one offspring without exposure).

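### The sibling inclusion rule in section 9.7.4, repeated in sensitivity analysis 11c, is broader than exploratory objective 6 and gives a comparison group that would differ by country

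*Protocol*

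**What the plan says.** Objective 6 appears in the same terms in the PASS Information table, the Abstract and section 8. It describes risk factors and outcome frequency in "paternally and maternally matched exposure-discordant (valproate vs lamotrigine/levetiracetam monotherapy) siblings at conception".

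Section 9.7.4 gives the rule for building that sibling set: "families with paternal valproate exposure-discordant siblings will be included (at least one offspring with paternal valproate exposure and one offspring without exposure". The stated purpose is to look for unmeasured family-related confounding, and the methods are summary cohort characteristics and the univariate analysis of section 9.7.3.1. Sensitivity analysis 11c in section 9.7.5 repeats the rule for the narrow NDD outcome: "only families with paternal valproate exposure-discordant siblings will be included (at least one offspring with paternal valproate exposure and one offspring without exposure".

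Section 9.2.2 decides which pregnancies are in the data at all. For Norway and Denmark the paternal drug criterion is "Father with at least one AED in the data available". For Sweden it is "Father with at least one exposure to AED during 192 days prior to 28 days after LMP2 date".

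**The concern.** Objective 6 and the section that implements it define discordance differently. The objective fixes both sides of the contrast: valproate on one side, lamotrigine or levetiracetam on the other, each as monotherapy, with both parents shared. The implementing text fixes only that one sibling had paternal valproate exposure and another did not. A programmer working from 9.7.4 would build a different cohort from one working from section 8.

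This matters because of what the analysis is for. The primary comparison is valproate monotherapy against lamotrigine or levetiracetam monotherapy, and the sibling set is meant to show whether family-level factors could lie behind differences in it. Section 9.3.1 keeps polytherapy and switchers out of the comparative analyses, citing severity bias and uncertainty over which drug is associated with the outcome. A looser sibling rule lets them back in. Where the comparison sibling was conceived with no paternal treatment, the contrast within the family is treated against untreated disease, or disease before onset, and not one drug against another.

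**Working it through.** No power, event count or alpha is involved, and the plan gives no figure to reproduce. The check sets the texts side by side, with one piece of arithmetic on window lengths.

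**1. Objective 6 against the rule in 9.7.4 and 11c**

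| Element | Objective 6 (section 8) | Rule in 9.7.4 and 11c |
|---|---|---|
| Index sibling | Valproate | Any paternal valproate exposure |
| Comparison sibling | Lamotrigine or levetiracetam | No drug named |
| Monotherapy | Required | Not mentioned |
| Shared parents | Both | Families and siblings mentioned; condition not repeated |

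The general exclusions that open 9.7.4 concern maternal antiepileptic drugs, maternal epilepsy and, for the primary outcome, the child's own antiepileptic drugs or epilepsy. None restores paternal monotherapy or a paternal comparator drug.

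**2. What lack of exposure means here.** The phrase is not defined. It explains discordance in valproate exposure, so its natural meaning is without valproate. Usage elsewhere agrees: section 9.3.1 describes polytherapy as "including valproate among the exposed and excluding valproate among the unexposed", and sensitivity analysis 11b refers to "offspring paternally unexposed to valproate but exposed to other AEDs (any combination". On that reading the comparison sibling may have been conceived on:

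- lamotrigine or levetiracetam (as in the objective);
- another antiepileptic drug, or a combination without valproate;
- no antiepileptic drug, because the father had not started or had stopped.

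Only the first group, restricted to monotherapy, belongs to objective 6.

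**3. Which of these each country can supply.** The Norwegian and Danish criterion concerns the father and has no timing limit, so all three groups can be extracted. The Swedish criterion is tied to the individual pregnancy. Reading it as running from 192 days before to 28 days after LMP2:

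- Extraction window: 192 + 28 = 220 days.
- Exposure window: 3 months, about 91 days before LMP2.
- Extraction window outside the exposure window: 220 − 91 = about 129 days, made up of 192 − 91 = about 101 days before it and 28 days after LMP2.

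A Swedish pregnancy with no antiepileptic drug in the exposure window can enter only if paternal use fell in those 129 days. A pregnancy with none in the whole 220 days is not extracted. Sweden can still supply comparison siblings conceived on lamotrigine, levetiracetam or another antiepileptic drug.

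**4. Result.** Under the literal rule, the Norwegian and Danish comparison groups may contain untreated pregnancies that the Swedish group almost entirely lacks. Under objective 6 this country difference goes, because a pregnancy conceived on lamotrigine or levetiracetam meets the drug criterion in all three countries.

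**The case against.** The strongest defence is that the parenthesis is shorthand. The paragraph announces that it serves objective 6, and that objective states its contrast three times. It also sends the reader to section 9.7.3.1, whose groups are valproate and lamotrigine/levetiracetam monotherapy. This supports aligning the text with the objective, but it does not settle what the text means: objective 5 cites the same section for polytherapy groups, so the cross-reference fixes neither monotherapy nor the comparator.

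It can also be said that operational cohort rules belong in the statistical analysis plan. That would hold if the protocol were silent. Here it states a rule, twice, and the rule departs from its own objective.

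Other parts of the defence stand. The analysis is exploratory and descriptive, no sibling hazard ratio is planned, and section 9.9.2 already rules out conclusions on causal mechanism. Nothing primary or secondary depends on it.

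Two stronger readings are tempting and are not supported. A reader might infer that the analysis sets on-treatment against off-treatment pregnancies. No text says the comparison sibling is untreated; the literal group is a mix, and the Swedish limit touches only its untreated part. A reader might also infer that the same-mother condition has been dropped. It has not been repeated, which is different: the text still speaks of families and sibling matching, and the objective still requires both parents.

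**Conclusion.** The inclusion rule in 9.7.4 and 11c contradicts objective 6 by being broader than it. Read literally, it admits valproate polytherapy and comparison siblings conceived on other antiepileptic drugs or on none. The untreated ones could appear in Norway and Denmark but hardly at all in Sweden, so the comparison group would differ in make-up by country and would not mirror the primary drug comparison.

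The size cannot be given: the documents contain no counts of discordant families and no split of comparison siblings by treatment. The country difference rests on reading lack of exposure as lack of valproate, and on reading the Swedish window as 192 days before to 28 days after LMP2. The mismatch with the objective rests on neither.

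The harm is limited to an exploratory, descriptive analysis and its repeat for the narrow outcome. It should be corrected, because the correction is cheap and a different contrast would otherwise be reported under objective 6.

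**What to change.** In 9.7.4 and in sensitivity analysis 11c, replace the parenthesis with the definition in objective 6: same mother and same father, at least one offspring with paternal valproate monotherapy, and at least one with paternal lamotrigine or levetiracetam monotherapy, each in the 3-month window before LMP2.

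Table 1 shows that final reports have already been submitted, so the sponsor should also state which rule was programmed and re-run the sibling tables if it was the broader one.

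The cost is a wording change and, at most, a re-run of descriptive tables. The drawback is fewer qualifying families. In Denmark, results with fewer than five cases or observations are withheld by the data provider (section 9.9.1), so some cells may be lost. This should be stated openly in the report.

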### 9.7.5 Sensitivity analyses

The following sensitivity analysis will be conducted:

1. *Variation of exposure time window for primary outcome:* Examine the association between extended risk window of paternal valproate exposure (6 months) and NDD, including ASD, in the offspring to investigate if there is an effect of valproate exposure other than through the spermatogenic cycle.
2. *Outcome of interest restricted to ASD specifically (ignoring all other NDD diagnoses):* Investigate the risk of ASD in offspring paternally exposed to valproate (monotherapy), compared to lamotrigine or levetiracetam (composite monotherapy) treatment at the time of conception.
3. *Exclusion of offspring with a birth weight lower than 1000gr or born prior to 8th month of pregnancy, for primary outcome.* There are suggestions for evidence of association between preterm birth/low birth weight and NDD (47–49). If AEDs affect preterm birth and preterm birth affects NDD, this means that preterm birth could act as a mediator between AEDs and NDD. In the same way, if AEDs affect very low birth weight and very low birth weight affects NDD, this means that very low birth weight could act as a mediator between AEDs and NDD. Adjusting for a mediator introduces a bias, therefore this sensitivity analysis will be performed excluding extremely low birth weight, very preterm and extremely preterm newborns to explore the potential impact introduced by inclusion of this sub-population of offspring on the point estimate.
4. *Handling of missing diagnoses for CM outcome:* Since a lot of diagnoses/reasons for spontaneous abortions and stillbirth could be missing, due to under-reporting, a sensitivity analysis will be performed to investigate the risk of CM using a broader definition of the outcome. It will include all the ICD-10 codes of interest where available, as reported in section 9.3.2.2, for live births and spontaneous abortions/stillbirths as well as all spontaneous abortions/stillbirths without an ICD-10 code for the diagnosis/reason. The main advantage of this broader definition of the outcome would allow to include in the analysis under reported cases of CM, on the other hand missing diagnoses related to cases different from CM could be included.
5. *Simple pairwise comparison valproate vs lamotrigine and valproate vs levetiracetam in monotherapy.* Valproate, lamotrigine and levetiracetam are medications with similar indications but that may be systematically prescribed for different type of epilepsy (such as valproate for genetically determined epilepsy and lamotrigine for focal onset epilepsy) and potentially other indications (lamotrigine might be prescribed for bipolar disorder and levetiracetam is not). Moreover, they were licensed in different periods (levetiracetam since 2000; lamotrigine since early 1990s; and valproate since 1967 to

treat epilepsy and since 1995 to treat bipolar disorder) resulting in systematic different in the treated populations. With the objective to evaluate if there is a differential effect of using one or the other comparator, a supplementary analysis will be provided to contrast valproate paternal exposure to separately lamotrigine and levetiracetam paternal exposure for the purpose of both NDD and CM outcome:

- a. Describe the characteristics of mother, father and offspring for both the primary and secondary outcome cohort and separately for paternal monotherapy exposure to individual AEDs (valproate or lamotrigine or levetiracetam).
  - b. Investigate the risk of NDD, including ASD, in offspring paternally exposed to valproate (monotherapy), compared to lamotrigine (monotherapy) treatment at the time of conception.
  - c. Investigate the risk of NDD, including ASD, in offspring paternally exposed to valproate (monotherapy), compared to levetiracetam (monotherapy) treatment at the time of conception.
  - d. Investigate the risk of CM, in offspring paternally exposed to valproate (monotherapy), compared to lamotrigine (monotherapy) treatment at the time of conception, in Norway and Denmark only.
  - e. Investigate the risk of CM, in offspring paternally exposed to valproate (monotherapy), compared to levetiracetam (monotherapy) treatment at the time of conception, in Norway and Denmark only.
6. *Comparison of the PS-weighted model with the traditional covariate adjustment model:* A Cox PH regression model will be used to estimate the HR of NDD, including ASD, with 95% CI (using offspring's calendar age in years as the underlying timescale) in offspring paternally exposed to valproate monotherapy within 3 months prior to LMP2 date compared to the reference group comprised of offspring paternally exposed to lamotrigine or levetiracetam (composite monotherapy) in the same time period. A logistic regression model will be used to estimate the OR of CM with 95% CI in offspring paternally exposed to valproate monotherapy within 3 months prior to LMP2 date compared to the reference group comprised of offspring paternally exposed to lamotrigine or levetiracetam (composite monotherapy) in the same time period. The list of confounders to be included is reported in Table 4. Within-family dependencies introduced by multiple offspring per father will be accounted for using sandwich estimators. Different results are expected because two different set of variables will be used for the adjustment due to the inclusion of risk factors in the PS model to improve efficiency; (c) noncollapsibility of the two models (46,50–52) (“the conditional OR or HR does not equal the marginal OR or HR in the presence of non-null treatment effect, even in the absence of confounding and effect modification” (52)).
7. *Effect of paternal exposure to valproate on NDD in offspring exposed and unexposed to AEDs after birth, and/or diagnosed with epilepsy.* As reported in section 9.3.3.1 the neurodevelopmental effects of postnatal exposure to AEDs and/or diagnosis of epilepsy on risk of NDD are not completely understood. Therefore, in the primary analysis such children are excluded. A sensitivity analysis will be conducted to explore the impact on the risk of NDD, including ASD, in offspring paternally exposed to valproate (monotherapy), compared to lamotrigine or levetiracetam (composite monotherapy) treatment at the time of conception will be performed by including these offspring. Offspring exposure to AEDs and diagnosis of epilepsy between birth and the exit date will each be considered time dependent, and thus allowed to take place at any time during the follow-up period. However, after the first dispensation of AEDs, the offspring will be considered exposed until the exit date.

8. *Validation of the assumption that individuals are exposed to one DDD per day.* WHO DDD is the assumed average maintenance dose per day for a drug used for its main indication (i.e. epilepsy for valproate, lamotrigine and levetiracetam) in adults. This does not necessarily reflect the recommended or Prescribed Daily Dose. Therapeutic doses for individual patients and patient groups will often differ from the DDD as they will be based on individual characteristics (such as indication, age, weight, ethnic differences, type and severity of disease) and pharmacokinetic considerations. A comparison (ratio) between the distribution of estimated treatment durations (expected) and time between prescriptions (observed) will be provided with the caveat that this will necessarily be affected by the DDD methodology approximation. In order to partially overcome this limitation, this comparison will be provided separately for patients with and without an indication of epilepsy, as epilepsy is the main indication for the medicines at study therefore the indication used by WHO to estimate DDD. It is expected that the use of WHO DDD will be a better approximation of the observed treatment duration among patients with a diagnosis of epilepsy, with a ratio closer to one than for other indications. The distribution of estimated treatment durations (expected) will be compared to the distribution of time between prescriptions (observed), *separately for lamotrigine, levetiracetam, valproate and for patients with and without an indication for epilepsy*, using the following formulas:

Observed time between prescriptions for patient i is

$$\sum_{j=1}^{k-1} \text{days} (\text{prescription}_{j+1} - \text{prescription}_j)$$

where k is the number of prescriptions for each patient.

Expected treatment duration for patient i is

$$\frac{\sum_{j=1}^{k-1} n. \text{pkg in prescription}_j * n. \text{dosage unit in each pkg}}{\text{WHO DDD}}$$

where k is the number of prescriptions for each patient.

The ratio of Observed over Expected for patient i is

$$\begin{aligned} \sum_{j=1}^{k-1} \text{days} (\text{prescription}_{j+1} - \text{prescription}_j) / \frac{\sum_{j=1}^{k-1} n. \text{pkg in prescription}_j * n. \text{dosage unit in each pkg}}{\text{WHO DDD}} &= \\ &= \sum_{j=1}^{k-1} \frac{\text{days} (\text{prescription}_{j+1} - \text{prescription}_j) * \text{WHO DDD}}{n. \text{pkg in prescription}_j * n. \text{dosage unit in each pkg}} \end{aligned}$$

The ratio for the population

$$\sum_{i=1}^n \left( \frac{\sum_{j=1}^{k-1} \text{days} (\text{prescription}_{j+1} - \text{prescription}_j) * \text{WHO DDD}}{n. \text{pkg in prescription}_j * n. \text{dosage unit in each pkg}} \right) / n$$

where n is the number of patients and k is the number of prescriptions per patient.

Under the assumption of perfect compliance of each patient, if the Ratio for the overall population is between 0.8 and 1.2 then the WHO DDD is a good approximation of the reality; the more the ratio departs from the good approximation range the more the real daily dose prescribed diverge from the WHO defined daily dose. It is expected to have a good approximation to the reality for patients with the epilepsy indication for AEDs.

This measure will be affected both from the approximation of using the WHO DDD and the compliance of patients to the treatment. The less the compliance, the more the ratio departs from good approximation (0.8-1.2). Since the dose prescribed is not available, it will not be possible to assess what affected more the results.

Sensitivity analysis 8 will be performed only in the Primary Outcome Cohort for Descriptive Analyses

9. *Narrow case definition for secondary outcome - focus on CM in live births*: Since the population for analysis of the secondary outcome for Sweden is comprised of live births, the distribution of CM observed in this population is likely to reflect functional defects and minor morphological abnormalities, rather than major morphological abnormalities (usually associated with fatal outcome during gestation). A sensitivity analysis will therefore be performed on the corresponding live birth population for Norway and Denmark to describe the corresponding risk and underlying distribution of CM associated with live births.
10. *Continuous measure of cumulative exposure*: Investigate separately the risk of NDD, including ASD, as well as CM, in offspring paternally exposed to monotherapy treatment with valproate, lamotrigine or levetiracetam at the time of conception, using cumulative exposure to treatment. Cumulative exposure will be calculated as the total amount of DDD intake that a father is exposed to over the 3-months time window prior to LMP2 date, i.e. the sum of the DDD in all 14-day intervals as reported in Figure 8.
  - a. In order to account for potential differences in the association between the cumulative exposure and the outcome at study between different treatments, an interaction term of the continuous variable representing the cumulative exposure and the dichotomous variable representing the valproate or lamotrigine/levetiracetam group will be tested for in each logistic and Cox PH model.
  - b. The cumulative exposure variable will also be categorised empirically according to tertiles of the distribution to represent low, medium and high exposure to each of the three treatment groups separately, since the cumulative exposure pattern may be different for each treatment, plus thresholds cannot be defined a priori as cut-off points are not available by previous literature. For each exposure group (valproate, lamotrigine and levetiracetam) separately, a within-group analysis will be performed to study the dose-response relationship for each outcome by comparing high and medium exposure to treatment against low exposure to treatment as the referent category.
  - c. For each outcome, a pre-defined list of covariates based on final models of primary comparative analyses will be forced into each of the aforementioned logistic and Cox PH model to provide estimates adjusted for relevant confounders. Since the distribution of cumulative exposure and of relevant confounders within each exposure group could differ from those of the other exposure groups, the results from the three within-exposure group analyses for each outcome will not be comparable.
11. *Narrow case definition for primary outcome - NDD*: This sensitivity analysis will use a narrow NDD composite case definition according to the following ICD-10 codes:

Clinical Code Description	ICD-10
Intellectual disability - mild	F70
Intellectual Disability - Moderate	F71

Clinical Code Description	ICD-10
Intellectual Disability -Severe	F72
Intellectual Disability -Profound	F73
Other Intellectual Disability	F78
Unspecified Intellectual Disability	F79
Specific developmental disorders of speech and language	F80
Specific developmental disorders of scholastic skills	F81
Mixed specific developmental disorders	F83
Childhood autism	F84.0
Atypical autism	F84.1
Other childhood disintegrative disorder	F84.3
Asperger syndrome	F84.5
Other pervasive developmental disorders	F84.8
Pervasive developmental disorder, unspecified	F84.9
Other disorders of psychological development	F88
Unspecified disorder of psychological development	F89
Dyslexia and other symbolic dysfunctions, not elsewhere classified	R48
Hyperkinetic disorders	F90
Specific developmental disorder of motor function	F82

This sensitivity analysis for the narrow NDD composite case definition only will be conducted in three parts:

- a. Replication of the primary objective, with descriptive and comparative analyses as applied to the primary outcome cohort. Meta-analysis may be applied.
- b. Replication of exploratory objective 5, with summary cohort characteristics and univariate analysis (section 9.7.3.1) performed to describe the subgroups and the risk factors for the narrow NDD composite outcome for offspring paternally exposed to valproate in combination with other AEDs (AED polytherapy) and offspring paternally unexposed to valproate but exposed to other AEDs (any combination) at the time of conception.
- c. Replication of exploratory objective 6, with an exploratory sibling-matched descriptive analyses conducted on the narrow NDD composite outcome whereby only families with paternal valproate exposure-discordant siblings will be included (at least one offspring with paternal valproate exposure and one offspring without exposure).

